Lay Summary

- 1 * Provide a summary of the background and purpose of the study in language that can be understood by a person without a medical degree.
This proposal investigates an adaptive control approach that allows a novel ankle robot (anklebot) to be used with treadmill training to reduce foot drop and improve walking in chronic stroke survivors. Currently, stroke survivors with foot drop are trained to live with a cane or other assistive device, and often ankle-foot braces (AFO's) for safety. Neither of these solutions allows patients to practice with their affected ankle during walking to promote recovery. Our approach uses information about how patients are walking from step-to-step, and over weeks, to inform the robot if and when robotic assistance is needed. This allows the patient to gradually re-learn how to use the ankle in the actual act of walking, compared to performing separate therapy exercises that may not be as helpful in recovery, or walking alone without robotic help.

The aims of the study are to compare effectiveness of 6 weeks treadmill walking with the anklebot vs. the same amount of walking on a treadmill without robotic assistance. The hypothesis is that treadmill + anklebot will improve walking more than treadmill alone as measured by: by greater increases in gait velocity, better ankle lifting when stepping forward, higher push-off forces at the affected leg, and greater increases in the amount of walking at home. It is also expected that the anklebot + treadmill group will have greater improvements in balance as measured by: reduced postural sway, reduced uneven loading between the legs in quiet standing, and gains in clinical balance scales. Finally it is predicted that the above gains will be better retained by the anklebot group at 6 weeks and again at 6 months after training cessation.

ID: VIEW4E02805CF7000
Name: v2_Lay Summary

View: v2_Justification, Objective, & Research Design

Justification, Objective, & Research Design

If you uploaded a separate research protocol document in the 'Research Protocol' page, cite the applicable section and page numbers from that document in the answer boxes below.

- 1 * Describe the purpose, specific aims, or objectives of this research. State the hypothesis to be tested:

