This proposal investigates a novel ankle robot (anklebot) adaptive control approach integrated with treadmill training to reduce foot drop and improve mobility function in chronic hemiparetic stroke survivors. Currently, stroke survivors with foot drop are trained to live with a cane or other assistive device, and often ankle foot orthotics (AFO's) for safety. Neither mediates task-practice or neuromotor recovery.

We have developed an adaptive anklebot controller that detects gait cycle sub-events for precise timing of graded robotics assist to enable deficit severity adjusted ankle motor learning in the context of walking. Our Merit pilot findings show that 6 weeks treadmill training with robot (TMR) timed to assist swing phase dorsiflexion only, is more effective than TM alone to improve free-walking swing dorsiflexion at foot strike (+400%, +9.7°, N=4/group), floor-walking speed (21% vs. 9%), and the benefits are retained at 6 weeks post-training such that 3 of 4 participants no longer required their AFO's. Notably, swing-phase TMR training improved paretic leg push-off (277% vs. 2%), and center-of-pressure (CoP) sway on standing balance (-25% vs. +30%), indicating generalized benefits to other elements of gait and balance, beyond those robotically targeted toward foot drop.

This randomized study investigates the hypothesis that 6 weeks TMR is more effective to durably improve gait biomechanics, static and dynamic balance, and mobility function in chronic stroke survivors with dorsiflexion deficits, compared to TM alone. Aims are to determine the comparative effectiveness of 6 weeks TMR vs. TM alone on:

- 1) Independent gait function indexed by gait velocity, swing-phase DF, terminal stance push off, and 48-hour free-living mobility profiles.
- 2) Balance function indexed by measures of postural sway (CoP), asymmetric loading in quiet standing, peak paretic A-P forces in non-paretic gait initiation, and standardized scales (Berg Balance, Dynamic Gait Index, and ABC for Falls Efficacy) and;
- 3) Long-term mobility outcomes, assessed by repeated measures of all key gait and balance outcomes at 6 weeks and 6 months after formal training cessation.

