TMR sessions begin with a baseline visit to assess fitting of the robot along with ability for wearing the device on the treadmill. The latter is determined by having participants walk for a series of brief trials of 3-5 min without, and then with, the unpowered robot. These trials are used to set initial parameters to define the robot's output to match the subject's baseline gait. Participants then are ready to commence training. TMR training will follow a progression that targets 30-40 minutes at 60-70% heart rate reserve over the 6 weeks. The TMR training programs are individualized according to the participant's gait capacity, defined by peak heart rate (HR max) achieved during the baseline treadmill test. Training is started conservatively with at 40-50% HRR determined by a cardiologist according to the formula of Karvonen. Training target HR = $%(HR_{max} - HR_{rest}) + HR_{rest}$. Individuals unable to walk continuously will exercise intermittently for several minutes as tolerated, with interval rests, and advanced as tolerated with HR, blood pressure monitoring, and Borg Perceived Exertion to assess subjective cardiopulmonary exercise tolerance. TMR training velocity is advanced as tolerated by week 6 to a target intensity of 60-70% HRR. Fall prevention during TMR is assured with the use of safety harnesses in non-weight bearing mode and hand rail support as needed. Robot assistance follows a progressive approach matched to subject responses as well. To modify paretic ankle contributions to gait in TMR we increase DF assist levels to generate toe clearance in swing. After users adapt to this stimulus we seek to gradually reduce the robotic assist level and promote self-regulated toe clearance.

TMO training

TMO follows essentially the same progression and procedures as the TMR, with the exception that no robot will be utilized.

The TMO training is essentially the same as that proposed for the TMR group: 3x weekly for 6 weeks, with the same work progression based on heart rate reserve as currently described in the above TMR procedures section. This group will be re-tested on outcome measures after 6-weeks (18 sessions), but they will not undertake the retention tests.

- 2 * Describe all procedures already being performed for diagnostic or treatment purposes (if not applicable to the study, enter "N/A"):
N/A
- 3 * Describe the duration of an individual participant's participation in the study:

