Data are analyzed for normality and transformed as necessary. Robust and resistant analyses or non-parametric analyses are performed as required. Analyses of effects of interventions on gait and balance outcomes are performed using repeated measures group-by-time (GxT) ANOVA for data obtained at baseline, after 6-weeks training, and at 6-weeks and 6-months post-completion of training. Non-parametric statistics are used when appropriate. Post hoc testing is performed using Scheffe's test. Because traditional ANOVA and regression analyses eliminate subjects who are missing data from one or more time points these analyses are performed using SAS PROC MIXED that allow subjects with incomplete data to be included. Initial analyses are intention-to-treat. Subsequent analyses take compliance into account. Baseline data are used to examine predictors of treatment response. We include data analyses for each method to avoid redundancy.

ID: VIEW4E02806052800
Name: v2_Sample Size and Data Analysis

View: v2_Sharing of Results

Sharing of Results

- 1 * Describe whether results (study results or individual subject results, such as results of investigational diagnostic tests, genetic tests, or incidental findings) will be shared with subjects or others (e.g., the subject's primary care physicians) and if so, describe how it will be shared:
Typically quantitative results from robotic results and other functional measures will not be shared with the participant. If a medical problem is revealed during medical examination and screening the participant will be informed and study staff will make appropriate efforts to facilitate follow-up with the participant's primary care physician.

ID: VIEW4E02808C8D800
Name: v2_Sharing of Results

View: v2_Research with Medical Devices

Research with Medical Devices

You indicated on the "Type of Research" page that your study involves the evaluation of device(s) for safety or effectiveness or use of a HUD.

- 1 * List all devices to be used in this study:

Device Name	FDA Approved?	Labeled	IDE Number	IDE Holder
View IMT Anklebot	yes	yes	N/A	no
- 2 * Attach the device labeling or device manual for the devices being used in this study:

Name	Created	Modified Date
Anklebot manual	1/20/2015 2:05 PM	1/20/2015 2:05 PM
- 3 * Are you requesting a nonsignificant device risk determination by the IRB? (Applicable if the FDA has not issued an IDE and the device does not qualify to be IDE exempt.)
 Yes No

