Official Title: Adaptive Ankle Robot Control System to Reduce Foot-drop in Chronic Stroke

NCT02483676

April 12, 2019

Statistical Analysis Plan for the study of Ankle Robot to Reduce Foot Drop in Stroke

This document lays out the analysis plan we intend to use for the study of whether robot-assisted treadmill training will result in greater improvements in gait and balance among chronic stroke survivors with foot drop impairment.

1.0 Brief description of the design of the parent study.

After baseline data collection, eligible patients were randomized to receive either treadmill with anklebot (TMR) or standard treadmill TM alone. Randomization was based on permuted blocks in two strata defined by baseline gait speed. Subjects in each group were be expected to attend 3 sessions per week for six weeks. Follow-up data collection will occur at the end of the training session. Durability of the improvements will be measured by also collecting data 6 weeks and 6 months after the end of the intervention. The primary outcomes will be the outcomes measured immediately after the end of training.

2.0 Statistical Test of the Primary Hypotheses.

2.1 Outcomes. The main outcomes to be considered will be::

AIM 1

- peak DF swing angle (Var="Pk DF P-ank) (Primary Outcome)
- DF angle at foot strike (Var="AIC") (2nd Primary Outcome)
- Mean Gait Velocity (Var="Prefered Gaid Velocity w/o AD")
- A-P GRF Propulsion (Var="AP impulse")

AIM 2

- Extent of Postural Sway (Var="EO Sway Area" or "EC Sway Area")
- Peak paretic A-P forces during push-off nonparetic gait initiation (Primary Outcome for Aim 2. (Var="Gait Initiation Peak NP A-P force") (Not collected for last 10-15 patients)

All these outcomes will be treated as quantitative random variables.

2.2 Analysis Sample. The primary analysis will be based on the principle of intention to treat. That is, in the analysis, patients will be included in the group to which

they were randomized, irrespective of whether they actually received the intervention. This provides anunbiased estimate of the causal impact of assigning a patient to TMR vs. assigning them to TR. The principle of intention-to-treat will be violated to the degree that outcomes for some patients at some timepoints are missing. The implications of missing data and how we will handle that are discussed below. Secondary analyses (described below) will be performed to using different analysis samples to estimate different causal parameters.

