2.3 Statistical Model. To estimate the impact of TMR vs TR, for each outcome, we will fit the following model:

E(Outcome)= β_0 + β_1 F1 + β_2 F2 + β_3 F3 + β_4 F1(TMR) + β_5 F2(TMR) + β_6 F3(TMR) + β_6 F3(TMR) + β_6 Covariates)

where F1, F2, and F3 are indicators for the three follow-up measures, and TMR is an indicator that the patient was in the TMR group. In this model, β_4 , β_5 , and β_6 stand for the difference between TMR and TR at each of the three follow-up time points. The primary analysis will be based on β_4 . This model will be fit using restricted maximum likelihood, allowing for different variancs at each time point, and different covariances between any two time points (this is sometimes referred to as an "unstructured" variance/covariance assumption). We will allow a different variance/covariance structure in each intervention group. However, if the differences in the estimated variance/covariance structures are not statistically significant (based on a likelihood ratio test), we will assume a common variance/covariance structure in the final model.

This model will provide valid inference if the distribution of outcomes does not markedly depart from normality. If an outcome appears to depart from normality by exhibiting a great deal of positive skewness (e.g., skewness coefficient greater than 3.0), I will fit the above model using a log-tranformed version of the outcome.

2.4 Covariates. Covariates will be included in the model if they are statistically significant (p<0.05) predictors of the outcome. This will reduce residual variation and increase power. Up to 3 covariates will be included in the model based on the strength of their statistical significance, chosen in a forward stepwise manner. Covariate will be chosen from the following candidate variables.

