3.0 Secondary Analyses

3.1 Intention to treat analysis of secondary outcomes. Similar analyses will be performed to explore the impact of TMR on the following secondary outcomes:

AIM 1

- Single support duration (Var="P-SS%")
- Double support duration (Var="DS%")
- Timing of peak fexion (Var="PK DF P-ank %cyc")
- Pareti foot vertical clearance (Var="p-foot clearance")
- Steps/day in two consecutive days (Var="48 hr Step Count ") (There seems to have been a lot of non-adherence regarding this measure and it may not be usable)
- Stroke Impact Scale (Var="SIS Mobility")

AIM 2

- coP trajectories of APAs during gait initiation by leg (Not measured)
- Berg Balance Scale (Var="Berg Balance")
- DGI scale (Var="DGI")
- ABC Scale (Var="ABC")

3.2 Per Protocol Analysis. In a secondary set of analyses, we will perform all of the above described analyses after including only those patients who attended at least 15 sessions in their assigned group. This results in an estimate of the causal impact of the TMR (relative to TM) among those willing and able to come to most of the sessions. We would expect to see a somewhat greater effect of TMR in this analysis because it will remove those who did not attend the TM sessions.

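### The Protocol exempts the treadmill-only arm from the retention tests that the comparative durability aim and SAP 2.3 require

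*Protocol*

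**What the plan says.** The documents call the control arm TMO, TM or TR; all three labels mean treadmill training without the robot.

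Under Protocol, Study Procedures item 1, TMO training, the control arm is tested after training and then no more: "This group will be re-tested on outcome measures after 6-weeks (18 sessions), but they will not undertake the retention tests".

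Four other places require control-arm data at both retention visits:

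- **Protocol, Lay Summary.** The prediction is that "gains will be better retained by the anklebot group at 6 weeks and again at 6 months after training cessation".
- **Protocol, Justification, Objective, & Research Design, item 1.** The stem of the aims reads "Aims are to determine the comparative effectiveness of 6 weeks TMR vs. TM alone on", and Aim 3 beneath it is "Long-term mobility outcomes, assessed by repeated measures of all key gait and balance outcomes at 6 weeks and 6 months after formal training cessation".
- **Protocol, Sample Size and Data Analysis, item 2.** A repeated-measures group-by-time analysis is planned "for data obtained at baseline, after 6-weeks training, and at 6-weeks and 6-months post-completion of training".
- **SAP 2.3.** The coefficients β4, β5 and β6 "stand for the difference between TMR and TR at each of the three follow-up time points".

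Two further places give the retention schedule without an exception for either arm: Functional motor assessments in Study Procedures item 1, and SAP 1.0. Either could be a general statement, so they support the point without proving it. Study Procedures item 3 (duration of participation) is ambiguous, because it speaks of robotics participants but places them in one of two training approaches.

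**The concern.** A claim that one arm retains its gains better needs both arms measured at the retention visits. The TMO sentence is current procedural text. It names the group, the test it receives and the tests it does not receive, and nothing elsewhere explains the exception.

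If staff followed it, one of the three aims loses its comparator, and so does the durability element of the main hypothesis. What remains is change over time in the robot arm, where true retention cannot be separated from the effect of repeated testing. If staff did not follow it, the Protocol still carries an uncorrected instruction that contradicts its own analysis plan.

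**Working it through.** **1. The plan's own figure.** Sample Size and Data Analysis item 1 gives 36 completers per group, with 85% power at 0.72 SD (two-sided 0.05) and at 0.90 SD (0.007). For a two-sample t-test the noncentrality is d × √(36/2), with 70 degrees of freedom.

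- d = 0.72: 0.72 × 4.243 = 3.05, power 85.4%.
- d = 0.90: 0.90 × 4.243 = 3.82, power 84.7% at 0.007.

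Both statements reproduce. They concern the post-training assessment only and do not depend on the retention visits.

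**2. What SAP 2.3 can estimate.** F1 is taken as the post-training visit, F2 as 6 weeks and F3 as 6 months after training. The printed formula repeats the F3(TMR) term; the repeat is dropped here and covariates are left out. The model then gives these means:

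| Visit | Control | TMR |
|---|---|---|
| Baseline | β0 | β0 |
| F1 | β0 + β1 | β0 + β1 + β4 |
| F2 | β0 + β2 | β0 + β2 + β5 |
| F3 | β0 + β3 | β0 + β3 + β6 |

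With both arms tested throughout, the design has rank 7 for 7 coefficients, and all are estimable.

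Under the TMO sentence the control cells at F2 and F3 are empty. Five distinct means remain (baseline, control F1, and TMR at F1, F2 and F3), so the rank is 5 for 7 coefficients.

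- Estimable: β0, β1, β4, and the sums β2 + β5 and β3 + β6, which are the TMR arm's own change from baseline.
- Not estimable: β2, β3, β5, β6.

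The same four coefficients fail with one subject-level covariate added (rank 6 of 8, against 8 of 8 with both arms tested). They also fail with the duplicate term kept as printed (5 of 8, against 7 of 8).

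**3. Whether the missing-data argument helps.** SAP 2.5 relies on missing at random, and its example is one patient who lacks the second follow-up but has other visits. That works when other control patients are seen at the visit. If none is, the data hold no information on the control mean there, and no likelihood method can supply it.

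**4. Effect on the primary contrast.** This uses generalised least squares with 36 per arm and assumed compound-symmetric or AR(1) correlations of 0.3 to 0.9.

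- F1 complete: the standard error of β4 is unchanged (ratio 1.000).
- 4 of 36 per arm missing F1 (assumed): losing the control retention data multiplies it by 1.002 to 1.013, an increase of 0.2% to 1.3%.

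**5. Which schedule was used.** Visit counts give a weak clue. The Protocol has about 4 pre-training visits, 18 sessions, and 2–3 visits for the first post-test round. Assume the same 2–3 visits for each retention round.

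- Before retention: 4 + 18 + 2 = 24, or 4 + 18 + 3 = 25.
- Full follow-up: 4 + 18 + 6 = 28, or 4 + 18 + 9 = 31; 29 or 32 if the robot-fitting visit is separate.

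Payment Detail item 3 pays for 24 visits and then for visits 25–28, with no exception by arm. That matches full follow-up only at the low end, and the section never says what visits 25–28 are.

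The SAP, dated April 2019, describes randomization in the past tense and notes other gaps. Gait-initiation force (SAP 2.1) is marked "Not collected for last 10-15 patients". Of the step count (SAP 3.1) it says "There seems to have been a lot of non-adherence regarding this measure and it may not be usable". Centre-of-pressure trajectories are listed as not measured. It records no gap for control-arm retention.

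**The case against.** The best counter-argument is that the sentence is probably left over and did no harm. The SAP is later than the Protocol form, whose uploads date from 2015. It describes durability data without an arm exception and defines arm contrasts at all three follow-ups. The payment split of 24 and 28 visits fits retention testing for everyone at 2 visits per round. This is a fair reading, and it may be the likelier one. It is still inference: the SAP's gap notes concern individual outcome variables, not visits or arms, and SAP 1.0 still puts follow-up in the future tense. Nothing corrects the TMO sentence.

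A second objection is that the conflicts differ in strength. Aim 3 names no arm and becomes comparative only through its stem, and the planned mixed model accepts incomplete data. The Lay Summary and SAP 2.3 are indeed the firmest conflicts. But the stem governs Aim 3, and a mixed model that runs still cannot estimate the retention contrast without any control data at those visits.

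A third is scope: the enrolment figures (100 locally, 100 in total) show one site, and the primary analysis is untouched. Both points stand. They limit the importance of the finding and leave the contradiction in place.

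**Conclusion.** The contradiction is certain; harm from it is not. If the TMO sentence was followed, two of the three between-arm contrasts in SAP 2.3 (β5 and β6) have no control data and cannot be estimated, and Aim 3 loses its comparative part. That result does not depend on sample size, correlation or covariates; it needs only that no control participant was tested at those visits. If the sentence is stray, the problem is one uncorrected procedural instruction.

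In either case β4 and the power statement for the end of training stand. The 0.2% to 1.3% loss of precision arises only under the assumed missing F1 data. This is a moderate issue, confined to durability, and should be fixed.

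**What to change.** Establish from the study records which schedule was used, and report the numbers tested by arm and visit. Then reconcile the TMO training text with the Lay Summary, Aim 3, the data-analysis section and SAP 2.3, and clarify the reference to robotics participants in Study Procedures item 3.

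1. **Both arms tested:** correct the TMO text to say that both arms complete the outcome battery after training, at 6 weeks and at 6 months.
2. **No control retention data:** state in SAP 2.3 that β5 and β6 are not estimable, report retention as a description within the TMR arm, and withdraw the comparative durability hypothesis.
3. **Some controls tested:** keep β5 and β6, and report how many controls were not tested and why.

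The minimum cost is a record check and a text correction. If control retention testing can still be done, assume 2–3 visits per round: 2 × 2 = 4 to 2 × 3 = 6 visits each. For 36 control completers that is 36 × 4 = 144 to 36 × 6 = 216 visits, or $1,440 to $2,160 at the Protocol's $10 per visit, with staff time extra. If the window has passed and the data do not exist, the cost is the between-arm durability comparison.
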